Subject Follow-up	
Treated subjects will be assessed for primary safety through 30-days post-procedure. Primary performance will be assessed at at least 12-months post-procedure.
 
The minimum follow-up window will be at 12-months, with a maximum follow-up window at 24-months.

Primary Endpoint(s)	
Primary Safety Endpoint:
 
The composite safety endpoint includes surgical ablation procedure related to death, stroke (regardless of level of disability), myocardial infarction, and major bleeding events within 30-days of the index ablation procedure. Deaths beyond 30-days and through last follow up that are attributed to surgical ablation procedure or CRYOF will also be reported as MAEs.
 
The reported events will be adjudicated by an independent physician for severity and relatedness to device and/or procedure.
 
Primary Performance Endpoint:
 
The primary performance endpoint is freedom from any documented atrial fibrillation (AF), atrial flutter (AFL), or atrial tachycardia (AT) lasting >30 seconds in duration at the last follow-up visit in the absence of Class I or III AADs (with the exception of AADs at doses not exceeding those previously failed). The rhythm status used for evaluation of this endpoint will be derived from a 24-hours electrocardiographic rhythm monitoring. The minimum follow-up window is 12 months and maximum at 24 months.
 
Any of the following scenarios will be captured and reported as failure of this effectiveness endpoint:
 
 
• Any electrocardiographically documented AF, AFL or AT recurrences lasting >30 seconds in duration at the last follow-up visit (by 30 second 12-lead ECG or 24-hours continuous ECG monitoring);
 

	
 
• The use of either new Class I or III antiarrhythmic drugs or doses exceeding previously failed (i.e. prior to ablation) at the last follow-up visit;
 
• Any subsequent catheter ablation or surgical ablation treatment for AF, AFL or AT following the index surgical AF ablation procedure (except for treatment of right typical atrial flutter).
 

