### **3.2 Measures Taken to Avoid and Minimize Bias**

This is a single-arm study. All enrolled subjects would have had a surgical ablation with the CRYOF device. Study data will be monitored against relevant source documents. An independent physician will adjudicate the SAEs reported in the study and rhythm assessments will also be adjudicated by a core lab. Furthermore, to mitigate temporal bias, enrollment in the trial will be based on random selection of treated subjects. The sequence with which treated subjects will be invited to participate in the trial will be randomly generated by the sponsor and provided to each site.

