## **4 ENDPOINTS**

### **4.1 Primary Safety Endpoint**

This composite safety endpoint includes surgical ablation procedure related to death, stroke (regardless of level of disability), myocardial infarction, and major bleeding events within 30-days of the index ablation procedure. Deaths beyond 30-days and through last follow up that are attributed to surgical ablation procedure or CRYOF would be reported as Major Adverse Events (MAEs).

All MAEs will be adjudicated by an independent physician, thus maintaining the objectivity of the primary safety endpoint. A detailed definition of the MAEs is provided below:

- Excessive Bleeding: is defined as a major complication if it is subsequent to a device related or study procedure-related injury and is treated with transfusion or results in a 20% or greater fall in HCT. Transfusion for anemia or other pre-existing condition that cause a fall in HCT without acute bleeding will not be considered a Major Adverse Event. Documentation of the cause of the bleed, and transfusion, and/or 20% or greater drop in HCT.
- Myocardial infarction (MI): When low blood flow causes the heart to starve for oxygen. Heart muscle dies or becomes permanently damaged. Documentation of MI; the presence of any one of the following criteria: (1) detection of ECG changes indicative of new ischemia (new ST-T changes or new LBBB) which persist for more than 1 hr, (2) development of new pathological Q waves on an ECG, and (3) imaging evidence of new loss of viable myocardium or new regional wall motion abnormality.

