- Stroke: A stroke is an interruption of the blood supply to any part of the brain. Rapid onset of a focal or global neurological deficit with at least one of the following: change in level of consciousness, hemiplegia, hemiparesis, numbness or sensory loss affecting one side of the body, dysphasia or aphasia, hemianopia, amaurosis fugax, or other neurological signs or symptoms consistent with stroke. Duration of a focal or global neurological deficit  $\geq 24$  h; OR  $<24$  h if therapeutic intervention(s) were performed (e.g., thrombolytic therapy or intracranial angioplasty); OR available neuroimaging documents a new hemorrhage or infarct; OR the neurological deficit results in death AND no other readily identifiable non-stroke cause for the clinical presentation (e.g., brain tumor, trauma, infection, hypoglycemia, peripheral lesion, pharmacological influences). Diagnosis should be confirmed by a neurology or neurosurgical specialist utilizing a neuroimaging procedure (MR or CT scan or cerebral angiography) or lumbar puncture (i.e., spinal fluid analysis diagnostic of intracranial hemorrhage). Documentation of a stroke or CVA consisting of acute loss of neurological function caused by an ischemic event with residual symptoms at least 24 hours after onset confirmed by CT or MRI scan or cerebral angiography of acute neurological event.
- Transient Ischemic attacks (TIA): A transient ischemic attack is a "mini-stroke" caused by temporary disturbance of blood supply to an area of the brain, which results in a sudden, brief decrease in brain function. Clinical symptoms similar to stroke but last for less than 24 hours. Documentation of TIA neuroimaging without tissue injury consistent with acute loss of neurological function caused by an ischemic event with resolution of symptoms within 24 hours after onset.
- Death: Document cause of death and include autopsy findings if autopsy performed.

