## **7 ADVERSE EVENTS**

Safety data for the primary safety endpoint will be collected from the start of the index ablation procedure to 30-days post procedure. The primary safety endpoint will be an evaluation of the incidence of major adverse events (MAEs) listed in section 4.1 for the procedural to 30-day post procedure time period. Deaths beyond 30-days or through last follow-up that are attributed to the surgical ablation procedure or CRYOF would be reported as MAEs.

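### The primary safety composite is worded two ways (TIA, and major versus excessive bleeding), and section 7.6 makes no exception for hematocrit falls that meet the 4.1 bleeding definition

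*Combined protocol and SAP*

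**What the plan says.** **Components.** The synopsis lists death and "stroke (regardless of level of disability), myocardial infarction, and major bleeding events within 30-days of the index ablation procedure", and the opening sentence of 4.1 does the same. Neither mentions TIA. The detailed MAE definitions that follow in 4.1 have no entry called major bleeding. They have an entry for excessive bleeding, which counts if it follows a device- or procedure-related injury "and is treated with transfusion or results in a 20% or greater fall in HCT", and a separate entry for TIA ("Clinical symptoms similar to stroke but last for less than 24 hours"). Section 7.1.1 repeats excessive bleeding and pairs TIA with stroke. Appendix III (Vascular Definitions) defines major bleeding as fatal bleeding, critical-organ bleeding, shock or severe hypotension needing surgery, or overt bleeding with a hemoglobin drop of at least 5 g/dL or at least 4 units transfused.

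**What is tested.** Section 7 makes the endpoint "the incidence of major adverse events (MAEs) listed in section 4.1". Section 8.2.2 also points to 4.1 and compares the MAE rate with 15%. Section 8.3 plans on a rate of up to 8.5% and gives 15 of 150 as the highest passing count.

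**What is recorded.** For the first 48 hours, section 7.6 keeps certain expected events in source documents only. One is a hematocrit decrease without hemodynamic change that stays above 25% and needs fewer than 2 units of red cells. Section 7.5.1 exempts the 7.6 events from eCRF capture even when they may be related to the procedure or device.

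**What is adjudicated.** Section 4.1 says "All MAEs will be adjudicated by an independent physician". The synopsis says "The reported events will be adjudicated by an independent physician for severity and relatedness to device and/or procedure", section 3.2 says "An independent physician will adjudicate the SAEs reported in the study", and 10.8.3 opens by giving the adjudicator reported adverse events.

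**The concern.** There are two linked problems. First, a reader cannot tell from the text alone whether a TIA counts, or whether a related bleed given 2 units with no other severe feature counts. The second is an MAE under the 4.1 definition but is not major bleeding under Appendix III.

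Second, the recording rule can overlap with the endpoint definition. A site that follows 7.6 and 7.5.1 as written could leave a qualifying bleed off the eCRF, and adjudication starts from reported events. Sections 8.2 and 8.10 require both safety and performance to succeed. In a single-arm comparison with a fixed 15% goal, a missing MAE can only move the result toward a pass.

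**Working it through.** **1. Reproduce the plan's limit.** Inputs from 8.2.2 and 8.3: n = 150, goal 15%, one-sided exact α = 0.05, expected rate 8.5%. With X ~ Binomial(150, q), the limit is the largest c with P(X ≤ c | q = 0.15) ≤ 0.05.

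- P(X ≤ 15 | 0.15) = 0.0493, a pass
- P(X ≤ 16 | 0.15) = 0.0807, a fail
- P(X ≤ 15 | 0.085) = 0.794

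The stated limit of 15/150 is right, and 79.4% agrees with the stated 80% power after rounding. The sample-size arithmetic is not in dispute.

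**2. Can one event satisfy both 4.1 and 7.6?** Section 4.1 does not say whether the 20% fall is relative or in hematocrit points. Let B be the baseline hematocrit; 7.6 requires the final value to exceed 25.

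- Relative: 0.80 × B > 25, so B > 25 / 0.80 = 31.25.
- Absolute: B − 20 > 25, so B > 45.

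Examples, each after a procedure-related injury, within 48 hours, with no transfusion and no hemodynamic change:

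- 40 to 31: (40 − 31) / 40 = 22.5%, ending at 31. It meets 4.1 on the relative reading and fits 7.6.
- 46 to 26: 46 − 26 = 20 points, ending at 26. It meets 4.1 on the absolute reading and fits 7.6.

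A related bleed given 1 unit is arguable. It is under the 2-unit limit of the hematocrit item, but the separate transfusion item in 7.6 covers only transfusions not connected with an adverse event.

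**3. Effect on the safety test.** The documents give no rate of TIA, of such bleeds or of unrecorded events, so the loss k is an assumption. If exactly k subjects with an MAE (and no other recorded MAE) are missed, the study passes whenever the true count is at most 15 + k. At a true rate of 15%:

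| k missed | Effective limit | False-pass probability |
|---|---|---|
| 0 | 15 | 4.9% |
| 1 | 16 | 8.1% |
| 2 | 17 | 12.4% |
| 3 | 18 | 18.1% |

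One missed subject changes the verdict only when the true count is exactly 16. P(X = 16) is 0.0807 − 0.0493 = 3.1% at a true rate of 15%, and 0.8628 − 0.7940 = 6.9% at 8.5%.

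**The case against.** The text goes some way toward settling the component list. Section 4.1 presents its detailed definitions as the definition of the MAEs. Sections 7, 7.1.1 and 8.2.2 all refer to 4.1. The excessive-bleeding entry itself speaks of a major complication, which links the two terms. Appendix III is a general glossary that none of these sections cites. The detailed list is also the broader one, so using it raises the count. These points stand: the detailed 4.1 list is the natural operative one, and the argument about direction applies to the recording gap, not to the wording.

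On recording:

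- Section 7 says endpoint data are collected from the procedure to 30 days, with no 48-hour gap.
- Section 7.5.2 requires all SAEs to be reported, with no 7.6 exemption.
- The last sentence of 10.8.3 extends adjudication to all primary safety endpoints until exit.
- The closing note of 7.6 calls the list guidance and lets the investigator report anyway.
- Source documents are monitored (3.2, 10.5).
- The 7.6 item can be read as exempting a laboratory value and not the injury behind it. Routine bypass-related falls are not MAEs, because 4.1 requires a related injury.

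These points narrow the gap to non-serious, injury-related bleeds within 48 hours that have stable hemodynamics, hematocrit above 25% and fewer than 2 units. They do not close it. None says that an event meeting 4.1 overrides 7.6, the investigator's option is discretionary and not tied to MAE status, and 7.5.1 applies the exemption to related events.

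**Conclusion.** The concern holds and should be fixed. The synopsis, the 4.1 opening sentence and the Appendix III term conflict with the detailed 4.1 list and 7.1.1 on TIA and on the bleeding threshold. Sections 7.6 and 7.5.1 also allow a bleed that meets 4.1 to stay off the eCRF. Loss of an endpoint event is possible, not certain, and the number is unknown. The 8.1%, 12.4% and 18.1% figures are illustrations that assume exactly 1, 2 or 3 missed subjects at a true rate of 15%. The direction is certain: a missed MAE can only favor a pass, at a limit where one subject separates p = 0.049 from p = 0.081. Confidence is high that the texts conflict and that the exception is absent. How often this would matter in practice cannot be judged from the documents.

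**What to change.** 1. Bring the synopsis, the 4.1 opening sentence, the 4.1 definitions, 7.1.1 and 8.2.2 to one MAE list. State whether TIA counts and which single bleeding definition applies. The choice is the sponsor's. If the Appendix III term is not the one chosen, say that it is not used for the composite.
2. Confirm that the 15% goal and the 8.5% planning rate refer to that list.
3. State whether the 20% hematocrit fall is relative or absolute.
4. Add to 7.6, with a cross-reference in 7.5.1: *This list does not apply to any event that meets an MAE definition in 4.1; all such events are entered on the eCRF and adjudicated.*

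The cost is protocol wording, CRF guidance and slightly more chart abstraction of hematocrit and transfusion data. The procedures have already been done, so patient care does not change. The observed MAE rate may come out higher.

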#### **4.2 Primary Performance Endpoint**

The primary performance endpoint is defined as freedom from any documented AF, AFL, or AT lasting  $>30$  seconds at the last follow-up visit in the absence of Class I or III AADs (with the exception of previously failed AADs at doses not exceeding those previously failed)

The results of the 24-Hour electrocardiographic rhythm monitoring data used for the primary performance endpoint, will be evaluated by an independent core lab thus maintaining objectivity of the primary performance endpoint.

Subjects will be considered primary performance failures if any of the following conditions are observed:

- Any electrocardiographically documented AF, AFL or AT recurrences lasting >30 seconds in duration at the last follow-up visit (by 30 second 12-lead ECG or 24-hours continuous ECG monitoring);
- The use of either new Class I or III antiarrhythmic drugs or doses exceeding previously failed (i.e., prior to ablation) at the last follow-up visit;
- Any subsequent catheter ablation or surgical ablation treatment for AF, AFL or AT following the index surgical AF ablation procedure (except for treatment of right typical atrial flutter).

#### **4.3 Secondary Safety Endpoint**

Key Secondary Safety Endpoints include:

- Implantation of a permanent pacemaker post-procedure through the last follow-up period.
- Overall device or surgical ablation procedure related SAEs through last follow up.

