Secondary Endpoints	
Performance:
 
 
1. Freedom from any documented AF, AFL, or AT lasting >30 seconds at the last follow-up visit regardless of Class I or III AADs.
 
2. Freedom from any documented AF, AFL, or AT lasting >30 seconds at the last follow-up visit in the absence of Class I or III AADs.
 
3. Acute procedural success defined as documentation of sinus rhythm at the end of the procedure.
 
 
Safety:
 
 
1. Implantation of a permanent pacemaker through last follow-up if related to the device or surgical ablation procedure.
 
2. Overall device or surgical ablation procedure related SAEs through last follow up.
 

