### **6.2 Follow-up Assessments**

#### **6.2.1 12-Month Visit ( $\geq$ 12-months but $\leq$ 24-months post index ablation procedure)**

Subjects will be consented 12 to 24 months post procedure and will be provided with a 24-Hour rhythm monitoring device at that time. The post procedure follow-up assessment will include:

- NYHA Classification
- 24-Hr Rhythm Assessment
- Evaluation of AEs/SAEs
- Medications – class I and III AAD's and anticoagulants, including any adjustments
- Review cardioversion since last visit

Note: If a clinical site is capable of remote subject visits, a modified visit assessment may be conducted. Remote subject visits should include Telemedicine appointments with the Investigator, where feasible, to allow direct engagement with the study subject and to ensure complete data collection. Rhythm monitoring devices may be provided to the subject either during an in-clinic follow-up visit, or shipped to the subject for a remote follow-up visit as applicable.

If clinical site is NOT able to perform remote subject visits, an attempt will be made to schedule the study subject visit as close to the visit window as is possible.

Regardless of when the subject is consented, the following data will be collected by reviewing the subjects' medical records retrospectively. For retrospective visits that fall outside of the required windows, please refer to sections 6.2.9 (Unscheduled Visit) and 10.6 (Protocol Deviations).

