## 6.2.8 Schedule of Events

Trial Activity	Visit 1	Visit 2	Visit 3	Visit 4	Visit 5	
	Baseline (Within 30 days of index procedure)	Procedure	Pre-Discharge	30-days (Within 23-37 days of index procedure)	12-months (≥ 12-months but ≤ 24-months of index ablation procedure)	Unscheduled visit
Informed consent & Inclusion/Exclusion	X					
Demographics	X					
Medical/Surgical History	X					
AF Classification	X					
Vital History	X					
NYHA Classification	X			X	X	X
12 Lead ECG, if done 	X	X	X	X		X
Medications/AAD Adjustment Review 	X		X	X	X	X
Adverse Events (AEs/SAEs)		X	X	X	X	X
Echocardiogram (transthoracic), if done	X					
Cox Maze III		X				
Concomitant Surgical Procedure		X				
Cardioversion Review 		X	X	X	X	X
24-Hours Holter (or equivalent)					X	

 12-lead ECG performed will need to be 30 seconds in length.

 Class I/III AADs and/or OACs only

 At physician's discretion and per institutions Standard of Care (SOC).

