### **7.1 Definition**

#### **7.1.1 Major Adverse Event**

Events qualifying as MAEs as defined in section 4.1 include:

- Excessive bleeding
- Myocardial Infarction (MI)
- Stroke, TIA
- Death

Any condition that was recorded as pre-existing is not a MAE unless there is a change in the nature, severity, or degree of the condition.

Sick Sinus Syndrome (SSS) and the implantation of a pacemaker for treatment of SSS post procedure will not be recorded as a MAE since it is a known underlying condition for subjects with long-standing persistent AF undergoing cardiac coagulation procedures.

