## 7.2 Pre-Existing Conditions Versus Adverse Events

A pre-existing condition is defined as a medical condition that is present before the index ablation procedure and is to be reported as part of the subject's medical history. It must be reported as a new AE if the intensity, frequency, or the character of the condition worsens during the study treatment and the AE was determined to have the relationship to the study procedures and/or study devices.

To avoid confusing pre-existing conditions with AEs during data analysis, the study sites must make all attempts to provide start dates for all baseline medical conditions. Any pre-existing condition that now meets the stated criteria as an AE should be recorded on the AE CRF as an exacerbation of the pre-existing condition and the start date will be recorded as the time when the exacerbation occurred.

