### **7.5 Adverse Event and Device Deficiency/Device Malfunction Reporting**

#### **7.5.1 AE/ADE/UADE Reporting**

##### General AE Reporting

Safety surveillance and reporting starts as soon as the subject is enrolled in the clinical investigation. Safety surveillance and reporting will continue until the 12-Month follow-up visit has been performed, the subject is deceased, the subject concludes participation in the clinical investigation, or the subject withdraws from the clinical investigation. All adverse event data, including deaths and device deficiency data, will be collected throughout the time period defined above and will be reported to the Sponsor on a CRF. Additional information with regard to an adverse event should be updated within the appropriate CRF.

Except for those events listed in Section 7.6, AEs potentially related to the study procedure or AtriCure devices used in the study and other AEs that the PI determines as critical to safety evaluation will be captured on the eCRF. Standard medical terminology should be used when recording AEs.

In addition, the following information should be recorded:

- Onset Date
- Resolution date or date of death
- Intensity of the event
- Action Taken
- Outcome of the event
- Relationship of AE
- Indication of whether the event is serious

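### Permanent pacemaker implantation, a key secondary safety endpoint, has two definitions, no dedicated data item and no stated at-risk denominator, so its reported rate can be biased low

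*Combined protocol and SAP*

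**What the plan says.** **Definition.** Section 4.3 lists "Implantation of a permanent pacemaker post-procedure through the last follow-up period" among the key secondary safety endpoints, with no condition on cause. The synopsis lists "Implantation of a permanent pacemaker through last follow-up if related to the device or surgical ablation procedure".

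**Collection.** Neither the visit lists (sections 6.2.1 to 6.2.7) nor the Schedule of Events (section 6.2.8) mentions pacemaker status or implantation. AEs and SAEs are evaluated at the procedure, pre-discharge, 30-day, 12-month and unscheduled visits. Cardioversion, which is not an endpoint, has its own schedule row ("Cardioversion Review") and a look-back prompt at the 12-month visit ("Review cardioversion since last visit").

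**AE rules.** On sick sinus syndrome (SSS), section 7.1.1 says that "the implantation of a pacemaker for treatment of SSS post procedure will not be recorded as a MAE", on the ground that it belongs to the background disease. Section 7.2 requires a worsened pre-existing condition to be reported as a new AE when, in addition, "the AE was determined to have the relationship to the study procedures and/or study devices". Section 7.5.1 sends to the eCRF the AEs potentially related to the procedure or the sponsor's devices, and "other AEs that the PI determines as critical to safety evaluation will be captured on the eCRF". Three provisions are broader: section 7.1.2 counts worsening of a pre-existing condition as an AE without a test of relatedness, section 7.5.1 also says that all adverse event data are collected, and section 7.5.2 requires every SAE on the AE form.

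**Denominator.** Sections 5.3.2 and 5.3.3 have no criterion on a prior pacemaker, and the baseline list in section 6.2.2 asks for cardiac history in general terms. Section 8.1 makes the ITT population (everyone treated with CRYOF) primary for safety endpoints. Section 8.2.3 gives no method or at-risk set for this endpoint.

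**The concern.** Whether a pacemaker was implanted is a fact that can be read from a chart. Here it reaches the database only if the site records an AE, and part of the AE wording depends on the site's view of cause. A subject already paced at surgery cannot have a first implant, yet nothing takes that subject out of the denominator. Missed implants and paced subjects both push the rate down; neither pushes it up.

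Section 1.1.3 names the need for a permanent pacemaker as one of the morbidities that held back the cut-and-sew Maze, and section 1.1.5 says that the data are meant for regulatory submission. A rate whose numerator and denominator are both unsettled is hard to interpret in that setting.

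**Working it through.** The plan states no expected rate, goal or test for this endpoint, so there is no plan figure to reproduce. The check has two parts.

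**1. Does each kind of implant reach the database?**

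| Provision | New AV block or bradycardia, paced | Sinus node disease recorded before surgery, worsened, paced, judged unrelated |
|---|---|---|
| 4.3 (any implant) | counts | counts |
| Synopsis (related implants) | counts if related | does not count |
| 7.1.2 | AE | AE |
| 7.2 | not applicable | not required as a new AE |
| 7.5.1, eCRF filter | recorded if potentially related or critical | recorded only if the PI finds it critical |
| 7.5.1, all-AE sentence | recorded | recorded, if treated as an AE |
| 7.5.2, all SAEs | recorded if serious | recorded if serious, and if treated as an AE |
| 10.8.3, adjudication | reviewed if reported | reviewed only if reported |

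The first column is largely safe: Appendix III defines bradycardia partly by treatment with a permanent pacemaker, and an implant would ordinarily meet a seriousness criterion in section 7.1.3. The second column is where the provisions disagree. Section 7.1.3 defines an SAE as an AE that meets further criteria, so a site that uses section 7.2 to decide that there was no new AE may not reach section 7.5.2. Section 4.3 would count that implant.

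**2. How far could the rate move?**

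Inputs:
- N = 150, the planned enrolment (section 5.6) and the likely ITT denominator.
- r = risk of implant among unpaced subjects. The only rate in the documents is about 15% (section 1.1.3), and it is for cut-and-sew Maze III, a different technique. It is used for scale only, with 5% as a second assumed value.
- f = share already paced, and c = share of implants captured. The documents give neither; both are assumptions.

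Formula: events recorded = N(1 − f) × r × c. Divided by N, the reported rate is r × (1 − f) × c.

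| r | f | c | Reported rate |
|---|---|---|---|
| 15% | 0 | 100% | 15.0% (no bias) |
| 15% | 5% | 100% | 0.15 × 0.95 = 14.25% |
| 15% | 10% | 100% | 0.15 × 0.90 = 13.5% |
| 15% | 0 | 70% | 0.15 × 0.70 = 10.5% |
| 15% | 10% | 70% | 0.15 × 0.90 × 0.70 = 9.45% |
| 15% | 10% | 50% | 0.15 × 0.90 × 0.50 = 6.75% |
| 5% | 10% | 100% | 0.05 × 0.90 = 4.5% |
| 5% | 10% | 70% | 0.05 × 0.90 × 0.70 = 3.15% |

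The denominator effect alone is modest. With 10 of 150 subjects already paced and 21 implants, the at-risk rate is 21/140 = 15.0% (exact 95% CI 9.5% to 22.0%), against 21/150 = 14.0% (8.9% to 20.6%). Incomplete capture could matter more.

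**The case against.** The strongest reply is that AE and SAE review takes place at every visit from the procedure onward, that each AE record holds the action taken and the relationship, and that every SAE must be reported whatever its cause. The list of non-reportable early events in section 7.6 covers temporary pacing and bradycardia that needs no treatment, not permanent implants. An independent physician adjudicates all SAEs. This stands, and it rules out the reading that no visit collects pacemaker implants. What is missing is a dedicated item.

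A reader might also infer that the SSS sentence in section 7.1.1 removes these implants from safety reporting. It removes them from MAEs only. Moreover, section 7.2 defines pre-existing as present before the index procedure, so sinus node disease first seen afterwards does not fit it. The possible loss comes from section 7.2 and the eCRF filter, and other wording in the same chapter contradicts them. A gap is possible but not established.

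Under the synopsis definition, an implant correctly attributed to pre-existing disease is outside the numerator, so its absence is not bias. That also stands, and it is why the two definitions have to be settled first. It does not help the endpoint as section 4.3 defines it, and adjudication covers only events that were reported.

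Finally, the denominator is not stated. That paced subjects stay in it is inferred from the ITT definition and the absence of any exclusion. Section 8 allows further detail in a separate SAP, and the general cardiac history might identify these subjects.

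**Conclusion.** The point holds in a limited form. The endpoint has two incompatible definitions. Its ascertainment depends on AE wording that conflicts with itself and that, read narrowly, can drop implants that section 4.3 counts. No rule sets aside subjects who are not at risk.

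The reported rate can therefore be biased low. It is tempting to say that it is biased low by a known amount, but the documents do not support that: they give neither the share already paced nor the share of implants captured, and with nobody paced and full capture there is no bias. Under the assumed 15% risk, paced subjects alone (5% to 10%) bring the rate to 14.25% to 13.5%, and 70% capture alone brings it to 10.5%.

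The endpoint carries no hypothesis test or performance goal. Sections 8.2 and 8.10 rest study success on the two primary endpoints, so success is unaffected. The change is worth making because it is cheap and the endpoint is a key safety one.

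**What to change.** 1. Reconcile the synopsis with section 4.3 on whether the endpoint is any implant or related implants only.
2. Add one pacemaker item, taken from the charts, with its own Schedule of Events row. At Baseline: permanent pacemaker present before the index procedure (yes/no). At Pre-Discharge, 30 days and 12 months: implanted since the procedure (yes/no), with date, indication and adjudicated relatedness.
3. Count the endpoint from this item rather than from AE forms, and report all implants and related implants side by side. Relatedness is needed because an item without it could not deliver the synopsis version.
4. State in the SAP that the denominator is the subjects without a permanent pacemaker at baseline.

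The cost is one eCRF item from charts already under review and one SAP line. The denominator becomes slightly smaller, and the rate may look less favourable.
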